## 1.2 Bisphosphocin Nu-3

#### 1.2.1 General Information

BisphosphocinsTM were originally discovered by while conducting research in the field of antisense technology and attempting to kill bacteria using gene silencing. The initial compounds identified were protonated/acidified oligonucleotides that demonstrated bactericidal activity independent of nucleotide sequence. Further experimentation expanded the class to protonated/acidified nucleotides and derivative molecules that exhibit chemical stability, acid pH resistance, and nuclease resistance enabling formulations for oral, intravenous, pulmonary, and topical delivery. The lead compound, designated Nu-3, is a thymidine derivative that would be considered to be in the nucleotide analogue class of drugs (Figure 1). Experimental data has elucidated a non-receptor dependent mechanism of action involving disruption of the bacterial cell membrane causing depolarization and rapid cell death. BisphosphocinsTM have an extremely broad spectrum of activity in vitro testing against over 70 different bacterial strains carrying various antibiotic resistant markers. There is currently no known mechanism of resistance to the bisphosphocin class and because they were synthetically derived there is no natural pool of resistant bacteria. In addition, panelling the compounds against a number of strains with known antibiotic resistance or clinical isolates has failed to identify any cross-resistance or resistance mechanisms. The following preclinical pharmacological and toxicology data is provided as a brief summary of the activity of bisphosphocin Nu-3 to support its potential as a treatment for diabetic foot infections and this clinical protocol should be read in conjunction with the Investigator Brochure on the product.

Figure 1. Structure, Chemical Name and Chemical Formula of Bisphosphocin™ Nu-3

## 1.2.2 Pre-Clinical Pharmacology and Toxicology

## Specific Pharmacology

Initial experiments revealed that bisphosphocinsTM had an antimicrobial activity distinct from any currently existing antibiotic class. Extensive in vitro and in vivo experiments have been conducted to further define their activity, identify their mechanism of action, and begin to establish a dose range to allow entry in human clinical trials. An important factor to consider in the review of the following experimental results is that it is now known bisphosphocinsTM do not follow the simple inhibitory kinetic model of one compound binding to one target molecule of the current classes of antibiotics but a more complex kinetic model involving the binding of multiple molecules to a bacterium resulting in direct bacteria cell death. For this reason, the current hypothesis is bisphosphocinTM dosing in vivo will be based on total dose delivered and not on maintaining a circulating level above the minimum inhibitory concentration or at the site of infection to achieve an efficacy outcome because the molecules rapidly bind and kill bacteria as opposed to inhibiting growth. Therefore, the therapeutic effect of bisphosphocinsTM can be manipulated by not only controlling the dose but frequency and duration of treatment not because of the pharmacokinetics of the compound but due to the fact that each dose will result in a reduction of bacterial load. The following experiments are presented to further define, distinguish and compare the activity of the bisphosphocin class from traditional antibiotics in order to develop a comprehensive clinical plan to enable evaluation in humans. The majority of the experimental data presented in the following sections was performed in the laboratory of outside collaborators or researchers who then published their results or by independent Contract Research Organization following the current guidelines for antimicrobial testing. Due to the unique MOA of the bisphosphocinTM class some standard assays were modified to enable the evaluation which has been noted in the protocol. Table 1 and Table 2 summarizes the activity of Nu-3 in the standard MIC assay against bacterial pathogens commonly found in diabetic foot infections and against common fungal pathogens.

Table 1. Bisphosphocin Nu-3 Activity in a Minimum Inhibitory Assay according to CLSI Guidelines

Organism	Number of Strains	MIC mg/ml
Acinetobacter baumannii	N=15	5-10
Enterococcus faecalis, VRE	N=15	5
Enterococcus faecalis, VSE	N=15	5
Enterococcus faecium, VRE	N=15	5
Enterococcus faecium, VRE	N=15	5
Escherichia coli	N=15	10
Proteus mirabilis	N=15	5-10
Proteus vulgaris	N=15	5-10
Pseudomonas aeruginosa	N=5	2.5-5

Organism	Number of Strains	MIC mg/ml
Pseudomonas aeruginosa	N=15	5-10
Serratia marcescens	N=15	10
Staphylococcus aureus, MSSA	N=15	5-10
Staphylococcus aureus, MRSA	N=15	5-10
Staphylococcus epidermidis, MRSE	N=15	10
Staphylococcus epidermidis, MSSE	N=15	10
Streptococcus agalactiae	N=15	10

Table 2. Anti-fungal Activity of Bisphosphocin Nu-3

Yeast Strain	ATCC#	Drug Resistance	MIC mg/ml
			Nu3
Candida albicans	44373	5-Fluorocytosine	≤0.53
Candida albicans	44374		≤0.53
Saccharomyces pastorius	2366		≤0.07
Trichophytan mentagrophytes var. interdigitale	200099		5.0

Evaluation of Nu-3 Activity against Bacteria Established in Biofilm

and were designed to evaluate the activity of Nu-3 against bacteria established in biofilms which is increasing becoming associated with chronic infections 12,unpublished. Biofilm was formed in borosilicate glass tubes by standard methods and then treated with Nu-3 or kept as untreated controls. As shown in Table 3, Nu-3 was able to penetrate the biofilm and kill the bacteria as judged by the lack of growth in Nu-3 treated tubes.

Table 3. Bactericidal activity of Nu-3 against bacteria established in biofilm

			Treatment			
Bacterial Strain	Designation	Assessment			Nu-3 Exposure (10mg/ml)	
			Media	Control	10min	30min
		Growth	N.G.	1.1 x 10  cfu/ml	N.G.	N.G.
Klebsiella pneumoniae Kp-S1	Clinical	Biofilm		and the state of		
		Growth	N.G.	2 x 10  cfu/ml	N.G.	N.G.
Acinetobacter baumannii	Acinetobacter baumannii BAA-1605					
	aphylococcus epidermidis 35984	Growth	N.G.	2.7 x 10  cfu/ml	N.G.	N.G.
Staphylococcus epidermidis		Biofilm				0
	Growth	N.G.	5.2 x 10  cfu/ml	N.G.	N.G.	
Staphylococcus epidermidis	midis PCI1200	Biofilm			,	
Staphylococcus aureus	NRS684	Growth	N.G.	4.3 x 10  cfu/ml	5 x 10  cfu/ml	8.6 x 10  cfu/ml
		Biofilm	0	0		0
Staphylococcus aureus	NRS732	Growth	N.G	7.6 x 10  cfu/ml	N.G	N.G
		Biofilm	0	0	0	

#### Assessment of the rate of kill of Nu-3 in 0.85% normal saline:

Bacteria in the log phase of growth were collected by centrifugation, re-suspended in sterile saline (0.85% NaCl) at 1 x 10^5 CFU/ml. Nu-3 in sterile saline was added to a final concentration of 0.2 to 10mg/ml to the bacteria and the bacteria/Nu-3 mixture incubated at room temperature. At time points ranging from 5 to 60 minutes, aliquots were removed, diluted and plated onto TS agar plates for quantitation of the number of colony forming units (CFU's). After 24h at 37°C, the number of CFU's were determined and the Nu-3 concentrations and exposure times resulting in 100% kill were determined (Table 4).

Table 4. Time and concentration dependent activity of Nu-3 against biofilm forming bacterial strains.

Destantal Studio	Nu-3 Concentration					
Bacterial Strain	0.625 (mg/ml)	1 (mg/ml)	5 (mg/ml)	10 (mg/ml)		
K. pneumoniae Sp1	15 min		5 min			
K. pneumoniae Sp5		15 min	5 min			
A. baumannii BAA-1605	30 min		10 min	5 min		
S. aureus NRS684				60 min		
S. aureus NRS732				60 min		

#### Mouse Suture Wound Infection Model

Briefly, a 10cm length of suture was threaded onto a needle and soaked for 45 minutes in undiluted cultures of *S. aureus* cvcc2248 or *P. aeruginosa* cvcc 5668 at 35°C for 8 hours. The needle and sutures were removed, placed on filter paper, and dried at 4°C until implantation. A 1-cm long piece of suture was implanted under the skin in the shaved and washed mid-back of anesthetized animals using knots to secure it in place. An incision was made between the knots on top of the suture line with a scalpel. The animals were then divided into groups and treated as indicated at 4h and 8h post-surgery and then 3 times daily for 3 days with either placebo, Nu-3 or ciprofloxacin ointment. On Day 5 the animals were euthanized and a 1cm² area surrounding and including the wound was harvest for homogenization and CFU counts (Table 5). The initial inoculum (i.e. CFU of bacteria in 1 cm length of suture) was determined by vortexing 1-cm of suture in bacterial growth media and plating serial dilutions to obtain bacteria counts.

Table 5. Log reduction in bacterial cell counts in surgical wound model

Tuestanout	Mean Bacterial Count ± SD (Log10 CFU/Wound)			
Treatment	P. aeruginosa	S. aureus		
Initial Inoculation	$4.93 \pm 0.33$	$4.79 \pm 0.31$		
Untreated	$7.52 \pm 0.57$	$7.64 \pm 0.58$		
Glycerin	$7.34 \pm 0.27$	$7.47 \pm 0.34$		
5% Nu-3 in Saline	$5.62 \pm 0.61$	$5.23 \pm 0.5$		
5% Nu-3 in Glycerin	$5.07 \pm 0.53$	$4.51 \pm 0.55$		
Ciprofloxacin HCl Ointment	$4.82 \pm 0.58$	$5.63 \pm 0.31$		

Mouse Superficial Skin Polymicrobial Infection Model

Briefly, mice are pre-treated with cyclophosphamide four day prior to initiating the infection to suppress the immune system. The mice are anesthetized and kept sedated while the fur on the back dorsal surface is shaved using electric clippers followed by 'wet shaving' with a disposable razor. The skin is then sterilized with a betadine wash followed by alcohol swab and abraded with a +50 grit emery board that results in a smooth, red, shiny appearance with no bleeding. A droplet of the bacterial inoculum is placed directly on the abraded skin that contains *Pseudomonas aeruginosa* UNT034-1 (ATCC 27853) 6.35 Log10 CFU/ mouse and *S. aureus* UNT006-4 (smith) 5.65 Log10 CFU/ mouse. The infected area is treated with 50 microliters of varying concentrations of bisphosphocin Nu-3, gentamycin, mupirocin, or normal saline twice daily for 3 days. The mice are then euthanized, the area of infected skin excised, and the CFU of both bacteria is determined by culture or serial diluted samples of homogenized tissue (Table 6). The data shows that the top 5% dose of bisphosphocin Nu-3 results in a 1 log reduction in the CFU count of both *S. aureus* and *P. aeruginosa*.

 Table 6.
 Mouse Superficial Skin Polymicrobial Infection Bacterial Counts

		S. aureus		P. aeru	ginosa
Compound	Dose	CFU	SD	CFU	SD
	1.0 mg/mL	9.22	0.19	6.35	0.21
NHIO	10 mg/mL	8.78	0.24	6.81	0.23
NU3	20 mg/mL	9.00	0.27	7.08	0.19
	50 mg/mL	7.61	1.35	5.65	1.16
Gentamicin	0.3%	4.40	0.85	5.17	0.87
Mupirocin	2.0%	6.32	1.01	6.95	0.51
Vehicle	saline	8.73	0.25	6.3	0.42
	Day 4	8.72	0.52	6.68	0.69
Infection Control	4 hr	5.40	0.45	4.33	0.83

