#### **Study Design**

Multi center, Randomized Double Blind, Placebo-Controlled, Dose Escalating Study

Clinical investigation Objective(s) and Endpoint:

	Objective	Endpoint	Variable
Primary	To assess the safety and tolerability of escalating doses of topically applied bisphosphocin™ Nu-3	Treatment emergent events related to clinical investigation product	
 
Vital signs,
 
CBC analysis, CMP analysis,
 
Physical examination,
 

Secondary	• To assess the clinical and microbiological response to bisphosphocin™ Nu-3	

Reduction of pathogenic bacteria

Visual evaluation of the ulcer

	

Aerobic and anaerobic culture and sensitivity

DUSS Score

	• To support determination of the appropriate dose range of Nu-3 to be employed in future clinical studies.		

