#### 14 ASSESSMENT OF EFFICACY

### 14.1 Primary Efficacy Endpoint Assessment

The primary efficacy endpoint is to assess the microbiological response to bisphosphocin™ Nu-3 as determined by reduction of pathogenic bacteria following Nu-3 treatment. The microbiological assessments from the local lab will be used to measure aerobic and anaerobic culture and sensitivity at screening, after a single dose treatment (Day 1), after a second dose treatment (Day 2), after twice daily for 7 day treatment, at Day 15.

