#### Diabetic Foot Ulcer Wound Infection Score

Parameter	Wound Infection Score						
rarameter	0	1	2	3			
Purulent discharge	Absent			Present			
Nonpurulant drainage (serious, sanguinous)	Absent	Mild					
Erythema	None	Mild pink, barely perceptible	Moderate pale red, defined edges	Severe red to dark red			
Induration	None	Mild	Moderate	Severe			
Tenderness (sign)	None	Mild	Moderate	Severe			
Pain (symptoms)	None	Mild	Moderate	Severe			
Local Warmth (relative to uninfected contralateral foot)	Same	Mildly increased	Moderately increased	Severely increased			

An improvement in the DFI Wound Score will be used to indicate a clinical improvement of the wound and a change in the DUSS Score wound be used to indicate the healing of a small ulceration.

Microbiological Response Evaluations:

This assessment will be conducted on samples collected by the investigator on Visit 2, Visit 4, Visit 5, and Visit 6.of the study which will be cultured to determine: microbial load and identity of the infected pathogens or wound flora. The microbiological response will be determined by a comparison of the results pre- and post-treatment.

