## **8. EFFICACY ANALYSIS**

### **8.1 Definition of Efficacy Endpoints**

All efficacy endpoints will be summarized by visit and evaluated statistically at the end of the MAD portion of the study. Efficacy endpoints include:

- The proportion of subjects with a normal culture
- The change from baseline in the DUSS score
- The change from baseline in the DFI score
- The absence of each of the following as reported by the investigator on the CRF:
  - Purulent discharge
  - Nonpurulent drainage
  - Erythema
  - Induration
  - Tenderness
  - PainLocal warmth (no change)
- Data captured on the total wound size for each subject using the Aranz Medical Silhouette™ System:
  - Wound area (cm^2)

- Percentage of area reduction
- Perimeter (mm)
- Maximum depth (mm)
- Mean depth (mm)
- Volume (cm^3)
- Length (mm)
- Width (mm)

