## **8.2 Analysis of Efficacy Endpoints**

For each dose group, the proportion of subjects with a normal culture at the end of the MAD portion of the study will be compared to the proportion of subjects with a normal culture at the end of the MAD portion of the study for the combined placebo group using a Fisher's exact test. A subject with a normal culture at this time will be considered a success. Any subject with a missing value at the end of the MAD portion of the study will not be included in the analysis. A p-value less than 0.05 will be considered statistically significant and a p-value less than 0.0167, employing a Bonferroni correction for multiple comparisons, will be considered highly conclusive.

For continuous efficacy endpoints, data will be summarized descriptively at and a comparison using the Wilcoxon Rank Sum test between each of dose groups and the combined placebo group will be performed at each visit. For these endpoints, no imputation for missing values will be performed.

For categorical endpoints, a Fisher's exact test will be performed in a similar manner. Subjects missing a value for a secondary endpoint will be considered a failure (counted in the denominator) for that endpoint.

For all tests, a p-value less than 0.05 will be considered statistically significant and a p-value less than 0.0167, employing a Bonferroni correction for multiple comparisons, will be considered highly conclusive. Analysis for each secondary endpoint will be performed on the ITT population and the PP population.

Ulcer measurements and percentage of area reduction will be summarized descriptively by visit and statistical testing using a Wilcoxon Rank Sum test between each dose group and the combined placebo group. For all tests, a p-value less than 0.05 will be considered statistically significant. Analysis for each additional endpoint will be performed on the ITT population and the PP population.

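### The SAP tests only an undefined normal culture at the end of treatment, so it cannot register the partial reduction in bacteria that the protocol names as its microbiological endpoint

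*Protocol*

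**What the plan says.** **Protocol, endpoint.** The objectives table in the synopsis gives the microbiological endpoint as "Reduction of pathogenic bacteria". Section 14.1 assesses the response "as determined by reduction of pathogenic bacteria following Nu-3 treatment". Section 7 and section 16.5 instead speak of eliminating pathogens, and 16.5 compares each dose with placebo by uncorrected chi-square or Fisher's exact test.

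**SAP.** The only microbiology item in 8.1 is "The proportion of subjects with a normal culture". Section 8.2 adds: "A subject with a normal culture at this time will be considered a success". Each dose is compared with pooled placebo by Fisher's exact test at the end of the MAD portion. Missing cultures are left out, and the thresholds are 0.05 and 0.0167. Normal is not defined. In the same list, the DUSS and DFI scores are analysed as changes from baseline; the culture result is not.

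**Measurement.** Section 14.1 of the five-cohort protocol specifies culture and sensitivity testing at the local laboratory, with no count or growth grade. The three-cohort text in the same file (6.4.1, Microbiological Response Evaluations) has samples "cultured to determine: microbial load and identity of the infected pathogens or wound flora" and compares pre- with post-treatment results.

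**Preclinical.** Section 1.2.2 of the three-cohort text says that "each dose will result in a reduction of bacterial load". Of the mouse skin model (Table 6) it says: "The data shows that the top 5% dose of bisphosphocin Nu-3 results in a 1 log reduction in the CFU count of both" species.

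**The concern.** The protocol describes a drug that lowers bacterial load dose by dose and names reduction as the endpoint. The SAP reduces the result to yes or no. A subject whose load falls without clearing, or who clears some pathogens but not all, is counted with a subject who did not respond. Because the baseline culture is not used, a subject whose culture was already normal before dosing would count as a success; the inclusion criteria in section 9.1.1 do not require a positive culture. Leaving normal undefined also lets it mean no growth, no pathogen, or normal flora only.

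At stake is the secondary objective on microbiological response and, through it, the objective of supporting a dose range. That second objective needs a measure that can separate no effect, partial effect and clearance.

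**Working it through.** **1. Reproduce the stated 1 log (Table 6, log10 CFU, 5% = 50 mg/mL).** Against the untreated Day 4 control: *S. aureus* 7.61 − 8.72 = −1.11; *P. aeruginosa* 5.65 − 6.68 = −1.03. The figure reproduces. Against saline vehicle the falls are 7.61 − 8.73 = −1.12 and 5.65 − 6.30 = −0.65.

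**2. Same table at the SAP doses, against vehicle.**

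| Dose | *S. aureus* | *P. aeruginosa* |
|---|---|---|
| 0.1% | 9.22 − 8.73 = +0.49 | 6.35 − 6.30 = +0.05 |
| 1% | 8.78 − 8.73 = +0.05 | 6.81 − 6.30 = +0.51 |
| 2% | 9.00 − 8.73 = +0.27 | 7.08 − 6.30 = +0.78 |

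There is no fall at any of them. Table 5 (5% in saline against untreated) gives 5.62 − 7.52 = −1.90 for *P. aeruginosa* and 5.23 − 7.64 = −2.41 for *S. aureus*, with more than 5 log10 CFU left in each.

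**3. Chance that a sample with the 5% mouse counts would be culture-negative.** Normal model, Table 6 means and SDs, assumed detection limit L: P = Φ((L − mean)/SD).
- L = 2: *S. aureus* Φ((2 − 7.61)/1.35) = 0.002%; *P. aeruginosa* Φ((2 − 5.65)/1.16) = 0.08%.
- L = 4: 0.4% and 7.7%.

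**4. Fisher thresholds (two-sided).** With 8 active and 3 × 2 = 6 pooled placebo (SAP), and 0/6 normal on placebo:
- 4/8: (70 + 15)/1001 = 0.085
- 5/8: (56 + 6)/2002 = 0.031
- 6/8: (28 + 1)/3003 = 0.0097

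So 5/8 is needed for 0.05 and 6/8 for 0.0167. With 5 × 2 = 10 placebo (five-cohort protocol) and 0/10 normal, 3/8 gives 56/816 = 0.069 and 4/8 gives 70/3060 = 0.023.

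**5. Power if few treated cultures become normal.** With placebo at 0%, power is P(X ≥ 5) or P(X ≥ 4) for X ~ Bin(8, p). At p = 10% this is under 0.1% (8 v 6) and 0.5% (8 v 10).

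**6. Power over assumed rates.** The documents give no human rate for either arm, so these are assumptions. Each cell is 8 v 6 / 8 v 10, at 0.05.

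| Placebo normal | Active 30% | 50% | 70% | 90% |
|---|---|---|---|---|
| 0% | 6 / 19% | 36 / 64% | 81 / 94% | 99 / 100% |
| 10% | 3 / 9% | 21 / 37% | 52 / 71% | 86 / 94% |
| 20% | 2 / 4% | 11 / 18% | 33 / 45% | 69 / 83% |

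**7. What a load measure would give (simulated exact Wilcoxon, 3,000 runs).** On Table 6 means and SDs at 5% against vehicle: 47% (*S. aureus*) and 21% (*P. aeruginosa*) at 8 v 6; 55% and 30% at 8 v 10. For a 1-log effect with assumed SD 1, 1.5 or 2: 37, 18 or 11% at 8 v 6, and 47, 25 or 16% at 8 v 10. On the Table 6 rows for 1% and 2%, power to show a reduction is about 0 to 1%.

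**The case against.** The strongest points on the other side largely stand, and they limit the claim.

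- **The SAP follows the protocol's own analysis section.** Section 16.5 says eliminate and plans a categorical test. The conflict between reduction and elimination lies inside the protocol; the SAP took over one side of it.
- **5% is not an SAP dose.** The SAP analyses 0.1%, 1% and 2%, where Table 6 shows no fall. On those data a load measure would find nothing either. The partial-fall argument applies to the 5% cohort of the five-cohort protocol; Tables 5 and 6 did not test 10%. The two dose sets need reconciling in their own right.
- **The preclinical evidence is mixed.** Table 3 reports no growth after 10 mg/mL (1%) in five of six biofilm strains, and Table 4 reports complete kill at 10 mg/mL or less for all five strains listed. Section 1.3 of the three-cohort text warns that animal models mimic a chronic wound poorly. The trial also plans 1 + 2 × 7 = 15 applications against 2 × 3 = 6 in the Table 6 mice, and nothing in the documents says how the fall grows with repeated use.
- **A load endpoint may not be derivable**, since the five-cohort protocol asks for no count or grade.
- **This is a secondary objective in a pilot** with no sample-size calculation.

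A reader might infer that the microbiological test has almost no chance of showing an effect. The documents do not support that: it requires the 5% mouse counts to carry over to patients and an assumed detection limit, and step 6 shows high power if most treated cultures become normal. None of this removes the mismatch between the named endpoint and the single analysis.

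**Conclusion.** The mismatch stands. The protocol's named endpoint is a reduction; the SAP's only microbiological test is an undefined yes/no result at one time point, taken without the baseline culture, and it cannot register a partial reduction.

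The consequence is conditional. If human responses resembled the mouse results at 5%, few treated cultures would become normal. At rates of 10% or less, Fisher power is under 0.1% at 8 v 6 and at most 0.5% at 8 v 10. Over the wider assumed range it runs from near 0 to 99% or more. Low power is therefore a risk that the plan leaves open, not an established result. Nor should it be inferred that a graded measure would make the comparison well powered: at 8 v 6, step 7 gives 21 to 47% on the Table 6 5% inputs. This is worth changing because it is cheap and lets the trial address its stated endpoint.

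**What to change.** In SAP 8.1 and 8.2:

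1. Define a normal culture as one with no pathogen isolated, and fix before unblinding how pathogens are told from flora.
2. State whether the endpoint is reduction or elimination, and align the synopsis and sections 7, 14.1 and 16.5 of the protocol.
3. Keep the Fisher comparison of normal cultures.
4. Add one pre-specified change variable: the number of pathogenic species isolated, from the last pre-dose swab to Visit 4, each dose against pooled placebo by Wilcoxon rank sum. Culture identification already supplies it.
5. If all sites report a common growth grade or count, analyse change in that as a separate variable. Do not rank counts, grades and species numbers together.

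**Cost.** SAP wording, alignment of the protocol text, and one derived variable from swabs already scheduled at every visit. **Limits.** The species count registers clearing some pathogens but not a lower load of one that persists; only item 5 does that. Local-laboratory swab results are coarse and may differ between sites, and the added analysis remains low-powered at 8 v 6.
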